#### **9.7.2.2 Secondary Endpoint**

- Number of Serious Adverse Events (SAEs) during the study period

Number of Serious Adverse Events (SAEs) reported during the study period will be summarised together with the number of patients with any SAE. Furthermore, listings will be provided displaying all SAEs.

#### **9.7.2.3 Exploratory Endpoints**

- Number of AEs related to hepatic or renal function during the study period
- Number of AEs that are defined within the system organ class nervous system during the study period and/or Number of physician-identified AEs related to significant deviations from expected neurologic function during the study period

Protocol  
 NN7088-4029  
 UTN: U1111-1235-6007  
 EU PAS No.

~~CONFIDENTIAL~~

Date: 17 April 2020  
 Version: 2.0  
 Status: Final  
 Page: 31 of 49

**Novo Nordisk**

Number of these specific AEs during study period will be summarised together with the number of patients with any of these AEs. Furthermore, listings will be provided displaying all these specific AEs.

- Changes in laboratory parameters during the study period, including hepatic and renal function parameters.

Laboratory parameters will be summarised by visit. Furthermore, change from baseline (visit 1) will be summarised. Listings and individual over time profile plots (where deemed relevant) will be provided displaying laboratory parameters reported during the study period.

- PEG-plasma levels at study entry, after two years and at the end of study

PEG plasma level will be summarised by visit. Listings and individual over time profile plots will be provided displaying PEG plasma level reported during the study period.

- Number of FVIII treatment requiring bleeding episodes reported during the study period

Number of FVIII treatment requiring bleeding episodes reported during the study period will be summarised. Furthermore, listings will be provided displaying all FVIII requiring bleeding episodes.

Definition of a bleeding episode: Multiple bleeding locations occurring during the same event (e.g., due to a bicycle accident) or at the same time point will be counted as one bleeding episode. A bleeding which occurs within 72 hours after stopping treatment of a previous bleeding event at the same or a subset of the same anatomical location(s) is considered a re-bleed, and is not a new bleeding episode. If a bleeding event occurs in the same location later than 72 hours after stopping treatment of a previous bleeding event it is considered a new bleeding episode.

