## 9.1 Study design

This is a prospective, multi-national, non-interventional post-authorisation study in patients with haemophilia A, prescribed prophylaxis with N8-GP by the treating physician prior to and independent of the decision to include the patient in the study. The study is designed to obtain additional real-life exposure and safety information.

The study is planned to include safety follow-up assessments at routine care visits for at least, but not limited to 5 years with 50 patients. Patients may continue in the study for the total planned study duration allowing active data collection for up to 7 years.

This study aims to observe routine use of N8-GP in any eligible patient in accordance with care prescribed by the treating physician, to the extent that enrolment of patients is allowed under local regulatory rules.

Monitoring of safety will be performed from a patient's first exposure to N8-GP after enrolment in this study defined by completion of informed consent through the patient's last visit in the study (defined as end of study or withdrawal of informed consent). Adverse events (AEs) are expected to be captured through the periodic clinical evaluations every 6-12 months that are routinely undertaken in patients with haemophilia A. Follow-up on any AE will be carried out until resolution of the AE, and if the patient discontinues to the extent allowed by IRB/ethics committees following discontinuation of the study. Exploratory assessment of the patients' PEG plasma level as requested by EMA, will be performed at pre-defined time points (see section [9.2.7.4](#)) and if considered clinically warranted by the responsible physician.

Protocol  
NN7088-4029  
UTN: U1111-1235-6007  
EU PAS No.

CONFIDENTIAL

Date: 17 April 2020  
Version: 2.0  
Status: Final  
Page: 18 of 49

Novo Nordisk

The follow up period after discontinuation of study drug should be as long as possible, preferably until end of study.

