**Novo Nordisk**

deviations from expected neurologic function during the study period

Changes in laboratory parameters during the study period, including hepatic and renal function parameters	From inclusion of the patient until end of study visit	Count of events
---	--	-----------------

PEG-plasma levels	At entry, after 2 years, and at the end of study	ng/mL
-------------------	--	-------

Number of FVIII treatment requiring bleeding episodes reported during the study period	As described in section 9.2.7.1	Count of events
--	---	-----------------

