**Novo Nordisk**

## 9.2.6 Visit procedures

**Table 9-1 Flow Chart**

Visit	Section	Baseline	Visits	Follow-Up
		Visit 1	Visit 2.1, 2.2, 2.3 etc	Visit 3 (End of Study)
PATIENT RELATED INFORMATION AND ASSESSMENTS				
Informed Consent	9.2.8.1	X		
In/exclusion Criteria	9.2.2 9.2.3	X		
Medical history	9.2.8.2	X		
Haemophilia treatment and bleed history	9.2.8.3	X		
Details of Haemophilia	9.2.8.4	X		
Demography	9.2.8.5	X		
Concomitant illness	9.2.8.6	X		
Concomitant medication	9.2.8.7	X	X	X
Withdrawal criteria	9.2.5		X	X
Genotype a	9.2.8.8	X		
Dosing regimen	9.2.8.9	X	X	X
Body measurements	9.2.8.10	X	X	X
EFFECTIVENESS				
Bleeding episode b	9.2.7.1	X	X	X
SAFETY				
FVIII inhibitor	9.2.7.2	X	X	X
Factor VIII Activity	9.2.7.3	X	X	X
PEG plasma level c	9.2.7.4	X	X c	X
Biochemistry	9.2.7.5	X	X	X
Urinalysis	9.2.7.6	X	X	X
Physical examination	9.2.7.7	X	X	X
Adverse event	9.2.7.8		X	X
OTHER ASSESSMENTS				
Surgery	9.2.8.11		X	X
REMINDERS				
Discuss content and use of patients own diary	9.2.7.1 , 9.2.8.9	X	X	
End of study				
	9.2.6.4			X

a) Only the FVIII genotype should be captured if available as existing result in medical records.

Protocol  
 NN7088-4029  
 UTN: U1111-1235-6007  
 EU PAS No.

~~CONFIDENTIAL~~

Date: 17 April 2020  
 Version: 2.0  
 Status: Final  
 Page: 23 of 49

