**Novo Nordisk**

- b) Only FVIII requiring bleeding episodes must be captured including bleed details and severity rating where available.
- c) One measurement two years after enrolment and if considered clinically warranted by the responsible physician.

Informed consent is required when entering the study. The rest of the assessments listed in the flow chart are not mandatory, but it is recommended to monitor safety of N8-GP in participating patients. Information from assessments performed during the patient's participation in the study should be recorded in the eCRF from the time informed consent has been obtained. For each visit the site personnel should enter all available information in the eCRF as specified in the below sections.

Patients should receive care at their respective clinic in accordance with local clinical practices. All study visits should be performed according to local clinical practice. The physician should keep a patient enrolment log and a log of patients evaluated for, but not included in the study, throughout the enrolment period. These logs may be separate or combined in one document. Patient identification is to be accomplished via allocation of a six-digit number which consists of a three-digit site code and a three-digit patient ID. A range of numbers will be provided by Novo Nordisk.

Signed informed consent must be obtained from the patient or, for patients under legal age, from the parent(s) or LARs prior to any study related activities.

Patients enrolled in the study should be provided with contact address(es) and telephone number(s) of the physician site and/or staff. In case a patient is being prematurely withdrawn from the study the physician should ensure that the procedures for the last visit are recorded, if possible.

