#### **9.2.7.5 Biochemistry**

If below biochemistry analyses are performed as a part of the local clinical practice, they should be recorded in the eCRF.

- Aspartate aminotransferase (AST)
- Bilirubin
- Creatinine
- Alanine Aminotransferase (ALT)
- Estimated Glomerular Filtration Rate (eGFR)

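### Laboratory values are to be summarised by visit, but interim visits are untimed sequence labels, so rows mix study times and late rows lose infrequent attenders

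*Protocol*

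**What the plan says.** Protocol section 9.7.2.3 sets the laboratory analysis in two sentences: "Laboratory parameters will be summarised by visit" and "Furthermore, change from baseline (visit 1) will be summarised". It adds listings and, where judged relevant, plots of individual patients over time.

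Table 9-1 defines a baseline visit, an open series "Visit 2.1, 2.2, 2.3 etc", and Visit 3 at end of study. The interim series has no target month and no window. Section 9.2.6 says: "All study visits should be performed according to local clinical practice". The only interval given is in section 9.1, which expects adverse events to be picked up at "periodic clinical evaluations every 6-12 months that are routinely undertaken in patients with haemophilia A". Section 9.2.7.5 makes the tests themselves conditional: "If below biochemistry analyses are performed as a part of the local clinical practice", the results go into the eCRF.

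Section 9.2.6.4 ties the end of study visit to the planned date of the last patient's last visit, and encourages patients who withdraw consent to attend one too.

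The table in section 9.1.3 lists "Changes in laboratory parameters during the study period, including hepatic and renal function parameters" and gives its unit as a count of events.

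**The concern.** A by-visit table reads as a time course only if a visit label stands for a time. Here an interim label says how many routine visits a patient has had. Two patients in the same row may be years apart in study time, and a patient appears in a high-numbered row only if seen often enough to get there before the study ends.

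What is at stake is the group-level picture of liver and kidney parameters over time. Section 8.3 names these parameters as a means of monitoring long-term exposure, and section 7 explains that the study arises from an obligation to investigate PEG accumulation. If attendance frequency differs between patients for any reason related to the values, such as centre, country, age or health, a drift along the visit axis may be created or hidden by who is in each row.

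Separately, a count of events cannot be the unit of an endpoint that is to be reported as values and changes from baseline.

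**Working it through.** **Inputs**

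- Interval between routine evaluations: 6 to 12 months (section 9.1).
- Follow-up per patient: 7 years in total with about 2 years of recruitment (section 4.4), so 7 − 2 = 5 to 7 years, or 60 to 84 months. The milestones, 03 June 2020 to 03 June 2027, agree with 7 years.
- Planned enrolment: 60 patients (section 9.2.1).

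The protocol gives no figure of its own to reproduce on this point.

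**1. When visit 2.k occurs.** If each of k intervals lies between 6 and 12 months, visit 2.k lies between 6k and 12k months after entry, and no later than month 84.

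| Visit | Earliest month | Latest month |
|---|---|---|
| 2.2 | 12 | 24 |
| 2.4 | 24 | 48 |
| 2.5 | 30 | 60 |
| 2.6 | 36 | 72 |
| 2.8 | 48 | 84 (8 × 12 = 96 is beyond the study) |

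Until the end of the study cuts the range off, every interim row spans a twofold range of time in study.

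**2. Who can reach visit 2.k.** The mean interval must be at most T/k, where T is the length of follow-up.

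- Visit 2.8: 84/8 = 10.5 months with the longest follow-up, 60/8 = 7.5 months with the shortest.
- Visit 2.10: 84/10 = 8.4 months and 60/10 = 6.0 months.

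A yearly attender has 60/12 = 5 to 84/12 = 7 visits, and a six-monthly attender 60/6 = 10 to 84/6 = 14, the last coinciding with the end of study visit. Rows from visit 2.8 on therefore contain no yearly attender.

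**3. How fast the rows change.** This illustrative simulation is scaled to 60 patients. It assumes a constant interval per patient, uniform between 6 and 12 months; uniform enrolment over 2 years; no dropout; and a test at every visit.

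| Visit | Contributors of 60 | Mean interval (months) | Share seen more often than every 9 months |
|---|---|---|---|
| 2.5 | 60 | 9.0 | 50% |
| 2.6 | 55 | 8.8 | 55% |
| 2.7 | 43 | 8.3 | 69% |
| 2.8 | 30 | 7.6 | 88% |
| 2.10 | 12 | 6.8 | 100% |

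If instead half the patients come every 6 months and half every 12, then from visit 2.7 on the contributors are in practice only the 30 six-monthly attenders. Under either pattern the selection starts after visit 2.5, whereas the mixing of times affects every interim row.

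**4. End of study visit.** It falls about 60 to 84 months after entry, and earlier for withdrawals. It is planned for everyone, so it does not select frequent attenders, but it too mixes durations.

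**5. The unit.** Section 9.7.2 summarises continuous data by mean, standard deviation, median, minimum and maximum, and section 9.7.2.3 adds change from baseline. Section 9.1.3 gives a count. The two do not describe the same quantity.

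**6. Check of the remedy.** Under the uniform assumptions of step 3, take the value nearest each anniversary of enrolment. Year 4 then covers months 43 to 53 with all 60 patients, the mean interval of contributors stays at about 9.0 months, and the share seen more often than every 9 months stays at 50% in every window. Numbers fall to about 30 of 60 in year 6, because of staggered enrolment and not attendance frequency.

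**The case against.** The protocol says by visit, not by visit number. Mapping irregular visits to time windows is ordinary SAP detail, and section 9.7 provides for a SAP before database lock. That is fair as far as it goes. But sequence labels are the only identifiers that interim visits have, the SAP is written only if found necessary, and the by-visit rule already stands in the protocol.

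The harm is also limited. Listings and, where relevant, individual plots show each patient's course whatever the visit label. Hepatic and renal adverse events are counted as an endpoint and are events of special interest (section 11.1), and cases meeting Hy's law are always serious events (Appendix A). Section 9.9 concedes that assessments have no fixed times and that this may affect interpretation. All of this stands. It reduces the consequence but does not repair the summary table.

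A reader might infer more than the documents support:

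- That frequent attenders are the patients with problems. The protocol does not say so; frequency may equally reflect centre, country or age.
- That the baseline to end of study change is also selected by attendance. It is not.
- That children and adults are simply pooled. Section 9.7.2 plans age subgroups.
- That renal function is missing in a comparable form. Estimated glomerular filtration rate is among the recorded variables (section 9.2.7.5).
- That windows could run from the first N8-GP dose. Previously exposed patients may enter (section 4.4), and section 9.2.8.3 specifies no first-dose date for collection.

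**Conclusion.** The point holds for the by-visit laboratory summary and for the unit. As written, each interim row spans about a twofold range of study time, and rows from visit 2.8 on cannot include a patient seen yearly. The month ranges rest only on the protocol's own 6 to 12 month expectation; extra contacts or visits without tests would widen them. The contributor counts depend on the simulation assumptions, but the direction of the selection needs only that attendance intervals differ between patients.

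The consequence is a poor time trend in one exploratory, descriptive summary. It does not follow that a hepatic or renal signal would be missed, because adverse event reporting and the patient-level displays do not depend on this table. The change is worth making because it is cheap and the stated rule does not suit the visit structure.

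**What to change.** In section 9.7.2.3, replace the by-visit rule for laboratory parameters with yearly windows from enrolment: one value per patient per window, the one nearest the anniversary, with the number of patients tested shown. Summarise change from baseline in the same windows. State that time since enrolment is not total N8-GP exposure for patients treated with the product before entry.

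In section 9.1.3, change the unit of the laboratory endpoint from a count to the laboratory unit and change from baseline.

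Optionally, add tables of shift from baseline to worst value for ALT, AST and bilirubin, using the multiples of the upper normal limit already in Appendix A (above 3 times for ALT or AST, above 2 times for total bilirubin), where local limits are recorded.

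The cost is protocol wording and a little more programming. No additional tests are needed. The windows are still fairly wide and some patients will have no value in some of them, which the number tested makes visible.

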### 4.3 Research question and objectives

The research question behind the study is to gain additional knowledge on safety in prophylaxis patients and obtain additional clinical data on the use of N8-GP in the setting of local clinical practice.

The primary objective of the study is to investigate the safety of N8-GP including the PEG moiety during prophylaxis and long-term use in patients with haemophilia A as prescribed by the physician.

Secondary objectives are to further evaluate the general safety of N8-GP during routine prophylaxis (including FVIII inhibitors and allergic/hypersensitivity reactions) and long-term use in patients with haemophilia A as prescribed by the physician.

Exploratory objectives are to monitor possible clinical effects of long-term exposure to N8-GP prophylaxis in patients with haemophilia A, including assessments of kidney and liver function parameters, neurological function and patients' PEG plasma level.

The primary endpoint of the study is:

- Number of Adverse Events (AEs) reported during the study period

The secondary endpoint is:

- Number of Serious Adverse Events (SAEs) reported during the study period

The exploratory endpoints are:

- Number of AEs related to hepatic or renal function during the study period
- Number of AEs that are defined within the system organ classes "Nervous system" or significant deviations from expected neurologic function during the study period
- Changes in laboratory parameters during the study period; including the hepatic and renal function parameters
- Changes in PEG-plasma levels from study start to end of study
- Number of FVIII treatment requiring bleeding episodes reported during the study period

Protocol  
NN7088-4029  
UTN: U1111-1235-6007  
EU PAS No.

~~CONFIDENTIAL~~

Date: 17 April 2020  
Version: 2.0  
Status: Final  
Page: 13 of 49

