**Novo Nordisk**

#### 4.4 Study design

This is a prospective, multinational, non-interventional PASS in patients with moderate or severe haemophilia A. Patients fulfilling the inclusion criteria can participate in the study regardless of previous treatment regimen, allowing inclusion of patients previously exposed to N8-GP and/or other FVIII products.

Patients will be treated with commercially available N8-GP according to local clinical practice at the discretion of the physician.

The total study duration is estimated to be 7 years with a planned recruitment period of approximately 2 years. The aim is to collect data on 50 patients on prophylaxis with N8-GP for at least, but not limited to 5 years. Patients may continue in the study for the total planned study duration allowing active data collection for up to 7 years.

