**Novo Nordisk**

adolescents and adults with severe haemophilia A (FVIII activity  $\leq 1\%$ ). The phase 3 trials documented that N8-GP is efficacious for prophylaxis and treatment of bleeding episodes across all age groups and in providing effective haemostasis during and after major surgical procedures. The median annualized bleeding rate for adolescents and adults was 1.18 and for children 1.95. In children, 82 % of their target joints did not bleed during the main phase of the trial, and children overall also showed an enhanced quality of life. The overall success rate for the first treatment of a bleeding episode evaluated within 8 hours was 88 %.

The general safety profile of N8-GP for the treatment of patients with haemophilia A is well examined through the clinical development programme, where N8-GP was well tolerated and has demonstrated a safety profile in the pivotal phase 3 trial in adolescents and adults, in the paediatric phase 3 trial and the surgery phase 3 trial similar to that of currently approved FVIII products.

The Committee for Medicinal Product for Human use (CHMP) has raised a theoretical concern regarding potential long-term effects of PEG accumulation in organs and other tissues. Based on modelling data and supported by analyses of PEG plasma levels in clinical samples from adolescent/adult and paediatric patients participating in the N8-GP phase 3 trials, plasma steady-state PEG concentrations have been reached in the clinical trial programme without any indication of PEG-related adverse effects to date. The clinical safety of long-term exposure to N8-GP – including evaluation of potential clinical consequences of exposure to 40 kDa PEG in organs and tissues – is yet to be established.

As per guideline, it is a request from the European Medicines Agency (EMA) to collect additional clinical data and to ensure consistency between the outcome from the pre-authorisation clinical trials and those from post-approval local clinical practice use of commercially available product. Therefore, a post-marketing investigation should be performed. Novo Nordisk has received an obligation to conduct a Post-Authorisation Safety Study (PASS) to investigate the potential effects of PEG accumulation in organs and other tissues.

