### 9.2.4 Rationale for selection criteria

The study is intended to reflect the population for which N8-GP is approved and marketed in the various countries, therefore study participants can be recruited regardless of their age as long as N8-GP is prescribed by the physician according to local label. In general, all patients from pre-authorisation clinical studies could be enrolled in post-marketing investigations.

Patients who previously developed inhibitors can be included after successful ITI. The proportion of ITI patients should not be more than 25% of the whole cohort.

The few inclusion and exclusion criteria will reduce selection bias. As a multicentre, multinational population has been selected the generalizability of the study is evaluated as high. The study is global and can include all ethnic groups.

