#### **9.2.6.1 Baseline (Visit 1)**

Relevant data available in the patient's medical record at the time of the baseline visit may be used as baseline data and should be entered in the eCRF after having obtained informed consent. All relevant data necessary for evaluating whether a patient can be enrolled in the study e.g. inclusion/exclusion criteria, see section [9.2.2](#) and [9.2.3](#), must be available prior to enrolling a patient. Relevant data regarding the assessments listed in the flow chart for visit 1 must be entered in the eCRF, if available.

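### Laboratory change from visit 1 pools new starters with patients already on N8-GP; record the first-dose date and show the change by prior exposure as well

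*Protocol*

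**What the plan says.** Section 9.7.2.3 summarises laboratory parameters by visit and adds: "Furthermore, change from baseline (visit 1) will be summarised". Listings are planned, with individual profile plots where relevant.

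Entry is open to patients with earlier exposure. Section 4.4 describes the design as "allowing inclusion of patients previously exposed to N8-GP and/or other FVIII products", and section 9.2.4 says that in general "all patients from pre-authorisation clinical studies could be enrolled in post-marketing investigations". For baseline values, section 9.2.6.1 lets relevant data in the patient's "medical record at the time of the baseline visit may be used as baseline data", with no stated window and no reference to the first N8-GP dose.

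Section 9.7.2 lists subgroups by age and by disease severity, with patients who had earlier inhibitors shown separately if needed. Prior N8-GP exposure is not listed. Section 9.2.8.3 asks for months spent on each type of regimen and the dosing used over the previous year; it asks for the product brand only when an inhibitor emerges. Section 9.2.8.9 records the N8-GP regimen at entry and later changes, with a date. Neither requires the date of the first N8-GP dose or the length of earlier exposure.

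For PEG, the abstract (section 4.3) names the endpoint as "Changes in PEG-plasma levels from study start to end of study". The endpoint table in section 9.1.3 gives levels "At entry, after 2 years, and at the end of study", and section 9.7.2.3 summarises levels by visit, with listings and individual plots.

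Section 7 states that the sponsor was obliged to run the study "to investigate the potential effects of PEG accumulation in organs and other tissues".

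**The concern.** The study has no control group, so within-patient change is its main quantitative contrast for liver and kidney function. That contrast is clear when visit 1 precedes N8-GP. For a patient already on treatment, visit 1 is a point partway along the exposure, and his later change measures only what remains.

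Averaging the two kinds of patient gives a figure with no single meaning. If an effect develops early and then levels off, the average is smaller than the change in new starters, and a mean near zero could be read as reassurance. If an effect appears only after long exposure, the already exposed may change more, and the average then describes neither group. Without a recorded start date the two kinds cannot be separated reliably afterwards.

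**Working it through.** The protocol states no calculated figure on this point. Section 9.5 sets 50 patients by regulatory request, without a sample size calculation. The question is therefore how far pooling could move the mean change.

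**Inputs**
- Exposed patients may enrol: sections 4.4 and 9.2.4.
- One baseline, visit 1, for all: section 9.7.2.3.
- p, the share already exposed at visit 1: not given, assumed 25%, 50% or 75%.
- f, the fraction of the eventual shift already present at visit 1: not given, assumed 0, 0.5 or 1.

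**Pooled change**

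Let D be the mean shift of a new starter over follow-up. An already exposed patient shows (1 - f)D after visit 1. The pooled mean is

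(1 - p)D + p(1 - f)D = D(1 - p*f).

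As a share of D:

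| | f = 0 | f = 0.5 | f = 1 |
|---|---|---|---|
| p = 25% | 100% | 87.5% | 75% |
| p = 50% | 100% | 75% | 50% |
| p = 75% | 100% | 62.5% | 25% |

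**What f might be**

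Assume a shift that follows 1 - exp(-t/tau), with 2 years of exposure before visit 1 and 5 years of follow-up. The exposed patient's remaining change relative to a new starter's is then exp(-2/tau), so f = 1 - exp(-2/tau).

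| tau (years) | remaining change | f | pooled share at p = 50% |
|---|---|---|---|
| 0.5 | 0.02 | 0.98 | 51% |
| 1 | 0.14 | 0.86 | 57% |
| 2 | 0.37 | 0.63 | 68% |
| 5 | 0.67 | 0.33 | 84% |

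A strictly linear effect gives f = 0 and no dilution. An accelerating effect makes f negative, so the pooled change exceeds the new-starter change.

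**What the split costs in precision**

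The 95% half-width of a mean change, in SD units, is t(0.975, n-1)/sqrt(n):
- n = 50: 2.010/7.071 = 0.28
- n = 25: 2.064/5 = 0.41
- n = 12: 2.201/3.464 = 0.64

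These are a guide to precision only; section 9.7.2 lists no intervals. They also assume that every patient has a laboratory pair, whereas section 9.2.7.5 records biochemistry only when it is done locally.

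**Why the pooled table should stay**

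Taking the same SD in both groups, the pooled mean is larger relative to its standard error than the new-starter mean when 1 - p*f > sqrt(1 - p), that is, when f < (1 - sqrt(1 - p))/p. For p = 25%, 50% and 75% this is f below 0.54, 0.59 and 0.67. Neither presentation is better throughout, so both are useful.

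**The case against.** The strongest reply is that this belongs in a statistical analysis plan. Section 9.7 leaves technical detail to such a plan, and an exposure split is an extra output that leaves the quoted sentence intact. That is fair for the tables. It does not settle the data gap: a later plan cannot reliably split on a start date that the protocol never asks for. Entry PEG level and the recorded regimen would help, but section 9.2.7.4 only prefers a sample at baseline. The case report form is not shown and may hold the date.

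A reader might infer that pooling shrinks every PEG-related shift. The documents do not support that: with f = 0 nothing is lost, and late effects could run the other way. A reader might also take the statement in section 7 that "plasma steady-state PEG concentrations have been reached in the clinical trial programme" as proof that exposed patients have nothing left to show. It concerns plasma, while the regulatory question concerns organs and tissues, so it does not establish f = 1. Nor does any text support a particular p; the protocol permits exposed patients without saying how many are expected.

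The open baseline rule in section 9.2.6.1 cuts both ways. A record value taken before the first dose gives an exposed patient a clean baseline, which is why its timing should be stated.

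Safeguards exist. Section 11.1 makes hepatic, renal and CNS events AESIs, Appendix A requires Hy's law cases to be reported as SAEs, and patient-level listings are planned. With about 50 patients, case review is workable. The PEG wording difference is minor, since change can be read from the planned individual profiles.

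**Conclusion.** The point holds in a conditional form. Visit 1 is fixed as the laboratory baseline for a cohort that may mix new starters with patients already exposed. No subgroup separates them, and the field needed to do so is not required. If part of a shift that levels off was present before visit 1, the pooled mean change shows 1 - p*f of the new-starter shift: between 50% and 100% at p = 50%, and between 25% and 100% over the whole assumed range. If few exposed patients enrol, or if f is near zero, the loss is negligible.

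The size rests entirely on assumed p and f. The endpoints are exploratory, no test or error rate is affected, and the primary endpoint of AE counts is untouched. This is a cheap improvement that makes the study's main organ-function contrast interpretable. It is not evidence that the planned summary will mislead.

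**What to change.** 1. In section 9.2.8.3, add the date of the first N8-GP dose, or the duration of prior exposure, to the baseline treatment history.
2. In section 9.7.2.3, keep the pooled table. Beside it, show change in ALT, AST, bilirubin, creatinine and eGFR separately for patients new to N8-GP and those already exposed at entry. State whether a record value used as baseline precedes the first dose.
3. Show PEG level and its change from entry by the same split. This also brings section 9.7.2.3 into line with the endpoint in section 4.3.
4. Label all of this descriptive and exploratory. Plots of PEG level against laboratory change are optional.

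The cost is at most one baseline field, a few sentences and a split of tables already planned. The downside is imprecision in small groups, about ±0.41 SD with 25 patients and ±0.64 SD with 12, so differences between the groups should be read with caution.
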